5.1.3 Additional Analyses

Additionally, in order to quantify the makeup of the group of subjects for whom the Device provides no result, the following proportions will be computed:

Metric	Probability of Interest	Computation
Proportion of "no result" with +ASD	$P(\text{Ref}=\text{+ASD} \mid \text{Cognoa}=\text{no result})$	$\frac{NRP}{NRP + NRN}$
Proportion of "no result" with -ASD	$P(\text{Ref}=\text{-ASD} \mid \text{Cognoa}=\text{no result})$	$\frac{NRN}{NRP + NRN}$

Two-sided 95% confidence intervals of each metric will be computed and reported.

5.2 Handling of Dropouts and Missing Data

The statistical analysis will be performed on an intention-to-diagnose basis [2]. Therefore subjects, once they have completed the consent process, will not be dropped from the study analysis. If a subject fails to complete the study for any reason, they will be retained in record-keeping and reported in the final analysis.

For any subjects that are missing the reference standard, both worst-case imputation and best-case imputation will be performed. Specifically, 2 sets of performance metrics and their 95% confidence intervals will be reported. They are as follows:

1. One set of outcome metrics will be reported with the missing reference standards assumed to be opposite to the device response ("worst-case").
2. One set of outcome metrics will be reported with the missing reference standards assumed to be the same as the device response ("best-case").

5.3 Covariate & Subgroup Analysis

Analysis of several covariates will be performed [3]. Specifically, the descriptive statistics for covariates of age, sex, race, ethnicity, parental level of education, and the clinical site of

enrollment will all be tabulated separately. The performance of the device will be reported separately for each covariate group and separate two-sided 95% confidence intervals will be computed and reported. However, the study will not be powered for any statistical inference on the covariates.

5.4 Sample size and power analysis

Cognoa plans to enroll 725 subjects in total. In prior studies of the device, dropout was identified as a potentially significant risk. Consequently, with a dropout rate of up to 25%, this total enrollment will ensure a minimum of 525 study completers.

In the intended population of use for the Cognoa device, based on prior studies with the device, we expect approximately 6% of subjects to be labeled +ASD by the device, 63% to be labeled -ASD, and 31% to get no result. With 525 study completers, we would expect approximately 32 to be labeled +ASD by the device, approximately 331 to be labeled -ASD, and approximately 163 to get no result. The following table summarizes these expected enrollment numbers.

Category	Expected Number of Subjects
Total Enrollment	725
Study Completers	544
Cognoa Test +ASD	33
Cognoa Test -ASD	343
Cognoa Test No Result	169

With these expected numbers of subjects, if 27 or more of the anticipated 33 Cognoa test positive subjects are found to truly be positive according to the reference standard then the PPV 95% confidence interval will have lower bound 68.7% and the primary endpoint's PPV performance goal will be met. Similarly, if 304 or more of the anticipated 343 Cognoa test negative subjects are found to truly be negative according to the reference standard then the NPV 95% confidence interval will have lower bound 85.3% and the primary endpoint's NPV performance goal will be met.

Cognoa expects the device to demonstrate PPV greater than 90% and NPV greater than 92%. With 90% PPV, there is a 96% chance that 27 or more of the anticipated 33 Cognoa test positive subjects will be found to truly be positive according to the reference standard. With 92% NPV, there is a 99% chance that 304 or more of the anticipated 343 Cognoa test negative subjects will be found to truly be negative according to the reference standard.

Therefore, the enrollment plan outlined above has greater than 80% power at a 95% confidence level.

Additionally, with the expected minimum 544 study completers we would expect approximately 169 to get no result from the Cognoa device and a "no result" proportion 95% confidence interval with range no greater than $\pm 7.5\%$.

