2.5 Statistical Framework

The first primary endpoint evaluates whether the device meets the pre-specified performance goals. This will be determined using two-sided 95% statistical confidence intervals. Other endpoints include the reporting of a number of metrics about the device's performance using 95% confidence intervals. For full specifications of the analysis of the endpoints, refer to section 5.1 *Analysis Methods* of this document.

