4 STATISTICAL PRINCIPLES

4.1 Confidence Intervals and P-values

In the analysis of the primary endpoints, 3 two-sided confidence intervals will be computed. Each endpoint will be evaluated at a 95% confidence level. The analysis of the first primary endpoint includes the computation of two distinct confidence intervals and two minimally

acceptable values that must be surpassed for the endpoint's performance goal to be considered met. In order to achieve a joint 95% confidence level for the entire endpoint, each of the two confidence intervals will be computed with a 95% confidence level and the lower end of the interval checked against the minimum acceptable value. This ensures a joint 95% confidence level on the conclusion that both measures evaluated in the first primary endpoint meet their minimum acceptable values. The second primary endpoint consists of a single confidence interval, which will also be 95% and two-sided.

All other confidence intervals presented will also be 95% and two-sided.

For full specifications of the analysis of the endpoints, refer to section 5.1 *Analysis Methods* of this document.

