5.1 Analysis Methods

5.1.1 Analysis of the Primary Endpoints

The Predictive Values of the device outcomes will be computed as:

Device Outcome	Probability of Interest	Computation	Minimally Acceptable Value
+ASD	$PPV = P(\text{Ref}=\text{+ASD} \text{Device}=\text{+ASD})$	$\frac{TP}{TP + FP}$	0.65
-ASD	$NPV = P(\text{Ref}=\text{-ASD} \text{Device}=\text{-ASD})$	$\frac{TN}{TN + FN}$	0.85

Two-sided 95% confidence intervals of each metric will be computed and reported. If both confidence intervals lie entirely above the minimally acceptable values, the endpoint will be considered to be met.

The proportion of all subjects who receive a "no result" outcome will be computed as:

Device Outcome	Probability of Interest	Computation
no result	$P(\text{Device}=\text{no result})$	$\frac{NRP + NRN}{\Sigma all}$

A two-sided 95% confidence interval around the metric will be computed and reported.

Note that the values used in the computation of the metrics used in the analysis of the primary endpoints are only defined for data-complete subjects. Therefore, in the analysis of the primary endpoints only subjects who complete the device assessment will be included. Additional analyses will be performed on subjects who drop out, as specified in section 5.2 *Handling of Dropouts and Missing Data* of this document.

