5.6 Statistical software

Statistical analysis will be performed using Python and R.

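### The SAP text available names no interval method for the primary endpoint, and the bounds printed in 5.4 are uncorrected Wald limits, which are too lenient for a two-sided 95% level

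*SAP*

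**What the plan says.** SAP 2.5 says of the performance goals: "This will be determined using two-sided 95% statistical confidence intervals". SAP 4.1 adds that "each of the two confidence intervals will be computed with a 95% confidence level", compares each lower end with its minimum acceptable value, and concludes: "This ensures a joint 95% confidence level on the conclusion". SAP 5.1.1 sets the minimum values at 0.65 for PPV and 0.85 for NPV and gives the decision rule: "If both confidence intervals lie entirely above the minimally acceptable values, the endpoint will be considered to be met".

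None of these sections says how the interval is computed. Section 5.6 says only: "Statistical analysis will be performed using Python and R". Protocol 11.3 defers to the SAP.

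The only worked intervals are in SAP 5.4. It begins "With these expected numbers of subjects, if 27 or more of the anticipated 33 Cognoa test positive subjects" are confirmed by the reference standard, "then the PPV 95% confidence interval will have lower bound 68.7" percent. For 304 or more of 343 device negatives, "then the NPV 95% confidence interval will have lower bound 85.3" percent. It treats both goals as met at those counts. It then gives a 96% chance of reaching 27/33 at a true PPV of 90%, and a 99% chance of reaching 304/343 at a true NPV of 92%.

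**The concern.** Success or failure depends entirely on two lower confidence limits. For a proportion, different 95% methods give lower limits several percentage points apart at n = 33, so the method is part of the decision rule. If it is not named, it can be chosen after the counts are known.

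The one clue, the pair of bounds in 5.4, points to the simple Wald interval. Wald limits for high proportions sit too close to the point estimate, so the lower limit clears the goal too easily. If the final analysis follows the planning figures, a device with a PPV of exactly 65%, or an NPV of exactly 85%, passes that component more often than the 2.5% implied by a two-sided 95% interval. The assurance in SAP 4.1 depends on each interval holding its level. Requiring both components does not cure this. The composite false-success rate is bounded only by the larger component rate, and it approaches that rate when the other measure is far above its goal.

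**Working it through.** **Inputs.** Goals 0.65 and 0.85 (SAP 2.2, 5.1.1); two-sided 95%, so 2.5% in the lower tail (2.5, 4.1); counts 27/33 and 304/343, printed bounds 68.7% and 85.3%, expected PPV 0.90 and NPV 0.92 (5.4).

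**Step 1: reproduce the plan's bounds.** Uncorrected Wald: p − 1.96·√(p(1−p)/n).

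- PPV: p = 27/33 = 0.8182; √(0.8182 × 0.1818/33) = 0.0671; 0.8182 − 0.1316 = 0.6866.
- NPV: p = 304/343 = 0.8863; √(0.8863 × 0.1137/343) = 0.0171; 0.8863 − 0.0336 = 0.8527.

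Both match 5.4. The power figures also reproduce: P(X ≥ 27 | 33, 0.90) = 0.958 and P(X ≥ 304 | 343, 0.92) = 0.989.

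**Step 2: compare other two-sided 95% methods at the same counts.**

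| Method | 27/33 lower limit (%) | 304/343 lower limit (%) |
|---|---|---|
| Wald | 68.66 | 85.27 |
| Wald, continuity-corrected | 67.14 | 85.12 |
| Arcsine | 67.08 | 85.06 |
| Jeffreys | 66.31 | 84.95 |
| Wilson | 65.61 | 84.83 |
| Agresti-Coull | 65.23 | 84.81 |
| Logit | 65.01 | 84.81 |
| Clopper-Pearson | 64.54 | 84.79 |
| Wilson, continuity-corrected | 63.92 | 84.67 |

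Only Wald gives the printed bounds. As bare counts, 27 and 304 are also the smallest passing counts under continuity-corrected Wald and arcsine. So the bounds, rather than the counts, identify the method.

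**Step 3: false-success at the planned counts** (exact binomial, true value at the goal).

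- PPV: P(X ≥ 27 | 33, 0.65) = 0.0283; P(X ≥ 28 | 33, 0.65) = 0.0102.
- NPV: P(X ≥ 304 | 343, 0.85) = 0.0320; P(X ≥ 305 | 343, 0.85) = 0.0219.

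Wilson also sets its PPV mark at 27/33, so at n = 33 the excess over 2.5% is discreteness and not specific to Wald. The NPV excess is specific to the lenient mark: Wilson and Clopper-Pearson both need 305.

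**Step 4: allow the group sizes to vary.** The numbers of device positives and negatives are random. Assumption: 544 completers, with binomial counts at the SAP's expected shares of 6% and 63%.

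| Method | PPV false-success | NPV false-success | PPV power at 0.90 | NPV power at 0.92 |
|---|---|---|---|---|
| Wald | 4.4% | 3.6% | 96% | 99% |
| Wilson | 2.1% | 2.2% | 93% | 98% |
| Clopper-Pearson | 1.6% | 2.1% | 91% | 98% |

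The false-success rates depend little on the assumption. With 525 or 544 completers, Wald PPV is 4.0–4.7% for a positive share of 5–8%, and Wald NPV is 3.6–3.7% for a negative share of 58–68%. Over the same ranges Wilson stays at 2.1–2.2% and Clopper-Pearson at 1.6–2.1%.

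Count by count, for 26 to 40 device positives (probability 0.82 under the assumption), PPV false-success exceeds 2.5% as follows:

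- Wald: at 15 of 15 counts (2.8% to 6.5%), and above 5% at n = 26, 27, 30, 34 and 37.
- Wilson: at 4 of 15 (maximum 3.0%).
- Clopper-Pearson: at none (maximum 2.4%).

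**Step 5: completer base (a separate point).** 725 × 0.75 = 543.75, so 544. The running text of 5.4 instead uses a minimum of 525, with 32/331/163 (525 × 0.06, 0.63, 0.31 = 31.5, 330.75, 162.75). The table said to summarise those numbers has 544 with 33/343/169 (32.64, 342.72, 168.64), and the last paragraph also uses 544.

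**The case against.** The best defence is that a Wald approximation in a sample-size section does not bind the final analysis, and that little depends on it. At the planned counts each mark moves by at most one subject. Under the SAP's own expectations, exactly 27/33 has probability 6.4% and exactly 304/343 has 0.6%. The claim of more than 80% power survives under any method proposed here. At 33 and 343, analysts who used a stricter method would visibly contradict 5.4, so their freedom is limited there. If the joint 95% statement in 4.1 is read as allowing 5% error, the Wald averages of 4.4% and 3.6% fall inside it. Wilson also exceeds 2.5% at some counts, including the planned 33.

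Most of this stands, and it limits the weight of the point. It does not remove it. The SAP states two-sided 95% intervals, which leave 2.5% below. Even on the 5% reading, Wald PPV exceeds the limit at 5 of the 15 counts examined. Wilson's excesses are small and due to discreteness, and its average stays below 2.5%; Wald's average does not. If strict control at every count is wanted, only Clopper-Pearson of the two options gives it. Section 5.4 fixes the verdict only for 33 and 343. Exactly 33 positives has a probability of about 7% under the assumption above, so the actual counts will probably fall where no available text fixes the method.

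Part of the SAP was not available for review, so the absence of a named method is established only for the text that could be read.

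**Conclusion.** The concern holds. In the available text the method that decides the primary endpoint is unstated, and the printed bounds are uncorrected Wald limits. Following them gives false-success of 2.8% (PPV) and 3.2% (NPV) at the planned counts, against a nominal 2.5%. The averages of 4.4% and 3.6% rest on binomial group sizes with 544 completers at the SAP's expected shares. The choice can decide the result: 304/343 passes under Wald and fails under both Wilson and Clopper-Pearson, and 27/33 fails under Clopper-Pearson.

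This should be fixed, but it does not undermine the design. The sample size remains adequate and the arithmetic attached to 27/33 and 304/343 is internally correct. The weakness is in the method and in its not being named. The 525 versus 544 mismatch is a real but separate inconsistency.

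**What to change.** Before unblinding, name one method in SAP 5.1.1 for the PPV and NPV intervals, and recompute the bounds, marks and power in 5.4 to match. Either of these is acceptable:

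- **Clopper-Pearson:** marks 28/33 (lower limit 68.1%) and 305/343 (85.1%). Power is about 89% and 98%, jointly 0.894 × 0.983 ≈ 88% if independent. False-success stays at or below 2.5% at every count.
- **Wilson:** marks 27/33 (65.6%) and 305/343 (85.2%). Power is about 96% and 98%, jointly 0.958 × 0.983 ≈ 94% if independent. False-success is below 2.5% on average, with small excesses at some counts.

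The two sets of marks must not be mixed. Merely ruling out Wald is not enough, because arcsine would keep the marks at 27 and 304.

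Separately, use one completer base throughout 5.4: 544 with 33/343/169, noting that these sum to 545 through rounding.

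The cost is wording and recalculation, with no extra subjects. At the planned counts PPV power falls from 96% to about 89% with Clopper-Pearson and is unchanged with Wilson; NPV power falls from 99% to 98% with either. The fix presumes that the blind is still intact. SAP 2.1 plans for this, but the revision's cover text confirms it only as of February 2020.

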5.6 Statistical software

Statistical analysis will be performed using Python and R.

